5.2.4. Diagnostic Assessments

22. presence of HBsAg or HBcAb at screening:

- Note: Evidence of HBV infection based on the results of testing at Screening for HBsAg.
- Patients who are negative for HBsAg should also be tested for anti-HBc, anti-HBs and HBV DNA and excluded according to the following algorithm:
- Participants negative for anti-HBs but positive for anti-HBc (negative HBsAg status) and positive for HBV DNA are excluded.
- Participants positive for anti-HBc (negative HBsAg status) and positive for anti-HBs (past and/or current evidence) are immune to HBV and are not excluded.
- Note: HBV DNA testing will only be performed during screening and prior to randomization for participants with positive anti-Hbc and both negative HBsAg and anti-HBs (past and/or current evidence).

23. Positive Hepatitis C antibody test result at Screening AND positive on reflex to Hepatitis C RNA.

- Note: Participants with positive Hepatitis C antibody due to prior resolved disease can be enrolled only if a confirmatory negative Hepatitis C RNA test is obtained (central lab will automatically reflex to HCV RNA on positive HCVAb).

24. Positive Hepatitis C RNA test result at Screening.

- Note: Test is optional and participants with negative hepatitis C antibody test are not required to also undergo hepatitis C RNA testing.

25. Any Grade 3-4 laboratory abnormality is exclusionary (with the exception of Grade 3-4 CPK and lipid abnormalities (e.g., total cholesterol, triglycerides, etc) following discussion and agreement by Sponsor Medical Monitor). A single repeat of any lab abnormality is allowed within a single Screening period to determine eligibility.

26. Alanine aminotransferase (ALT) $> 1.5 \times$ ULN and / or total bilirubin $> 1.5 \times$ ULN (isolated bilirubin $> 1.5 \times$ ULN is acceptable if total bilirubin is fractionated and direct bilirubin $< 35\%$). A single repeat of ALT and / or bilirubin is allowed within a single Screening period to determine eligibility.

27. Creatinine clearance (eGFR) of < 60 mL/min/1.73 m² using CKD-EPI equation (2021)

28. Any acute laboratory abnormality at screen which, in the opinion of the investigator, should preclude participation in the study of an investigational compound.

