7 DISCONTINUATION OF STUDY INTERVENTION AND PARTICIPANT DISCONTINUATION/WITHDRAWAL

7.1 Discontinuation of study intervention

‘Discontinuation’ of study intervention refers to any participant who has not received all planned doses of the study intervention. In rare instances, it may be necessary for a participant to permanently discontinue study intervention.

If study intervention is permanently discontinued, the participant should remain in the study, continue to comply with all other aspects of the protocol (such as starting the first dose of standard of care ART on Day 10) and be followed according to the SoA (Section 1.3) to the EOS as defined in the protocol.

If participants prematurely discontinue study treatment prior to Day 10 (primary endpoint), participants may be replaced at the discretion of the Sponsor in consultation with the investigator.

Participants will not be replaced if the reason for discontinuation from the study treatment is due to a safety concern which the investigator considers reasonably attributable to study treatment e.g., when a participant meets stopping criteria. Refer to Section 7.1.2 (Liver chemistry stopping criteria), Section 7.1.3 (QTc stopping criteria) and Section 7.1.5 (Suicidal ideation and behavior) and Section 7.1.6 (Hypersensitivity reactions).

A participant may be discontinued from the study intervention at any time if any of the protocol individual stopping criteria are met:

- Emergence of any positive (abnormal) CSSRS response, or participant report of suicidal ideation and behavior at any time during the study, confirmed by the investigator or a clinician (or qualified designee) during the monotherapy period.
- Pregnancy
- \geq Grade 3 AE (or clinically significant laboratory abnormality) suspected to be related to VH4524184.
- An SAE, regardless of its severity, that is considered to be clinically significant and reasonably attributable to dosing with VH4524184, in the opinion of the Investigator.
- A grade ≥ 2 rash with concurrent fever with or without concurrent elevations in liver biochemistry reasonably attributable to dosing with VH4524184, in the opinion of the Investigator.
- Emergent medical condition that is judged by the Investigator as to jeopardize the subject’s safety if he or she continues to receive the study drug.

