8.3.7 Study pausing rules

Participant safety will be continuously monitored by the Medical Monitor, designated Safety Lead (or delegate), throughout the study. Pertinent findings and conclusions are shared with the product's SRT for review of the overall benefit-risk profile of the product. The Sponsor's governance group, VSLC will review data and the team's recommendation when any pausing/stopping rules are met. The VSLC is comprised of senior representatives from various departments, including clinical development, safety, toxicology, pharmacovigilance, epidemiology, and medical affairs. The VSLC will govern whether enrollment may be resumed/modified, a given treatment arm will be stopped, or the study stopped. (See Section 10.1.6 for more details on VSLC)

The following study pausing criteria would be applied:

- Death of a participant, regardless of investigator's assessment of causality
- Any Grade 4 event or an SAE, regardless of its severity, that is considered to be clinically significant and reasonably attributable to dosing with VH4524184 in the opinion of the investigator or the Sponsor.
- Any Grade 3 or higher AE (of the same type) in 2 or more participants, leading to the decision to withdraw from the study (by the investigator), assessed by the investigator as reasonably attributable to VH4524184.
- Any Grade 2 or higher rash with evidence of systemic involvement (e.g., fever, liver transaminase elevation and/or eosinophilia) that the investigator considers reasonably attributable to VH4524184 occurring in two or more participants.
- Any Grade 4 laboratory abnormality (of the same type) or Grade 3 laboratory abnormalities (of the same type, with the exception of an asymptomatic Grade 4 lipid abnormalities or CPK increase) that the investigator considers reasonably attributable to VH4524184, in two or more participants.
- Any participant meeting liver stopping criteria that the investigator considers reasonably attributable to VH4524184.
- Any participant meeting QTc stopping criteria that the investigator considers reasonably attributable to VH4524184.
- Clinically significant arrhythmia in two or more participants.

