10.1.6 Committee structure

Participant safety will be routinely monitored by the VH medical monitor and the GSK safety lead(s). Pertinent findings and conclusions are shared with the product's SRT for periodic review of the overall benefit risk profile of the product and escalated, as necessary to VSLC.

An SRT is in place for each VH product. It comprises of a global cross-functional VH/GSK team responsible for the ongoing assessment of benefit-risk for a product. The SRT contribute to the continual blinded assessment of incoming new efficacy, safety and PK information. An external data and safety monitoring committee is not utilized in this study due to the relatively small size and early phase of the trial. This is further supported by the lack of significant safety findings from the available pre-clinical toxicity studies and preliminary clinical study of VH4524184.

VSLC is a governance group that will review data and the team's recommendation when any pausing/stopping rules are met. The VSLC will govern whether enrollment may be resumed/modified, a given treatment arm will be stopped, or the study stopped. The VSLC is comprised of senior representatives from various departments, including clinical development, safety, toxicology, pharmacovigilance, epidemiology, and medical affairs.

ViiV Healthcare has transferred certain sponsor obligations (e.g., clinical operations, study intervention management, data management, statistics and programming, clinical pharmacology and modelling and simulation, regulatory, pharmacovigilance, etc.) to GSK who are supporting VH in the conduct of this study.

Refer to the List of Clinical Laboratories and Key Vendors document for the names and addresses for the clinical laboratories, contractors and subcontractors used by VH in this study.

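### The laboratory pausing rule puts an exception for Grade 4 lipid values in the Grade 3 bracket, so read literally it exempts either no lipid value or only the more severe ones

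*Protocol*

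**What the plan says.** The laboratory bullet in protocol section 8.3.7 has three pieces.

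- A Grade 4 arm: "Any Grade 4 laboratory abnormality (of the same type) or". Its bracket holds no exception.
- A Grade 3 arm, whose bracket does hold one: "Grade 3 laboratory abnormalities (of the same type, with the exception of an asymptomatic Grade 4 lipid abnormalities or CPK increase".
- A closing condition for both arms: "that the investigator considers reasonably attributable to VH4524184, in two or more participants".

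Two other bullets in the same list bear on the point. One covers "Any Grade 4 event or an SAE, regardless of its severity, that is considered to be clinically significant and reasonably attributable" to dosing, in the opinion of the investigator or the sponsor, with no minimum number of participants. The other covers "Any Grade 3 or higher AE (of the same type) in 2 or more participants, leading to the decision to withdraw from the study", again when judged attributable.

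A similar exception appears in exclusion criterion 25 (section 5.2.4), which bars Grade 3-4 laboratory abnormalities at screening "with the exception of Grade 3-4 CPK and lipid abnormalities", provided the medical monitor agrees. The SAP does not restate the pausing rules.

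**The concern.** The exception and the clause that it qualifies name different grades. Removing Grade 4 lipid values from a set of Grade 3 abnormalities removes nothing. If a reader instead gives the exception effect by applying it to the values it names, the more severe lipid result is exempt and the less severe one pauses the study.

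The CPK wording adds a second uncertainty. The limits to asymptomatic and to Grade 4 both stand before the lipid term, and the text does not say whether either carries over to CPK.

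This is an operative threshold. When a pausing rule is met, the sponsor's safety and labelling committee reviews the data and governs whether enrollment resumes, an arm stops or the study stops. Section 10.1.6 adds: "An external data and safety monitoring committee is not utilized in this study". Sites and the sponsor should reach the same answer from the same laboratory values. The values can arise: fasting lipids and CPK are required tests (section 10.2), and chemistry is drawn on Days 1, 2, 4, 7 and 10 and at each follow-up visit (section 1.3).

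**Working it through.** The plan gives no figure to reproduce, so the check applies the wording case by case. The inputs are the three pieces of the bullet in section 8.3.7. The cases are asymptomatic values, judged attributable, of the same type and in two or more participants.

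Two choices are open to a literal reader: whether the exception stays within the Grade 3 bracket or is applied to the values it names, and whether the Grade 4 limit governs lipids and CPK or lipids only. That gives 2 × 2 = 4 literal readings.

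| Reading | Lipid Grade 3 | Lipid Grade 4 | CPK Grade 3 | CPK Grade 4 |
|---|---|---|---|---|
| 1. In bracket; Grade 4 governs both | pause | pause | pause | pause |
| 2. In bracket; Grade 4 governs lipids only | pause | pause | exempt | pause |
| 3. Applied to values named; Grade 4 governs both | pause | exempt | pause | exempt |
| 4. Applied to values named; Grade 4 governs lipids only | pause | exempt | exempt | exempt |

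- In readings 1 and 2, Grade 4 lipids pause through the unqualified Grade 4 arm, and Grade 3 lipids pause because they are not Grade 4. The lipid exception does nothing.
- In readings 3 and 4, Grade 4 lipids are exempt and Grade 3 lipids pause. Severity is inverted. Reading 3 inverts it for CPK as well.
- Reading 2 exempts Grade 3 CPK while Grade 4 CPK pauses. That order is coherent, but the lipid half still has no effect.
- If the symptom limit does not reach CPK, a symptomatic CPK increase could also be exempt from this bullet in readings 2 to 4.

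Other text that might settle the matter:

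- Exclusion criterion 25 names Grades 3-4 for both analytes, but it governs screening and depends on medical monitor agreement.
- Section 10.3.6.2 says that an asymptomatic Grade 4 laboratory value is not automatically serious. That concerns SAE status, not pausing.
- The Grade 4/SAE bullet does not reach a non-serious Grade 3 value. The Grade 3 AE bullet requires a decision to withdraw from the study.

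None of these restates or corrects the exception.

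**The case against.** The strongest reply is purposive: a sponsor that tolerates asymptomatic Grade 4 lipids must also tolerate milder Grade 3 ones. On that reading all four cases in the table are exempt and nothing is inverted. It is a sensible guess at intent, and the grades in exclusion criterion 25 lend it some support. It therefore cannot be said that Grade 3 lipids pause under every possible reading; they pause under the literal ones. But the text does not state this exemption, and a safety threshold should not depend on inferring it.

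The second reply is that little is at risk, and most of it stands. A clinically significant, attributable Grade 4 event pauses after one participant, which is stricter than the laboratory bullet. Section 7.1 allows individual discontinuation for an event at or above "Grade 3 AE (or clinically significant laboratory abnormality) suspected to be related to VH4524184", and says that the sponsor reviews safety data as they arrive, singly and together. Section 10.1.6 lets findings be escalated to the governance committee as necessary, so a pausing rule is not the only route to review. For CPK, section 10.2 recommends repeat testing of elevated values, and section 5.3.3 bars strenuous exercise for 48 hours before safety blood draws.

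A third reply is that exempting Grades 3-4 of both analytes loosens the rule. It does, compared with every literal reading, so that wording needs the sponsor's decision.

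**Conclusion.** The bullet is wrong as written, and the point is minor. A Grade 4 exception sits in a Grade 3 bracket. Literally it exempts either no lipid value or only asymptomatic Grade 4 lipids, and the treatment of CPK is open in both grade and symptom status.

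The size is limited to attributable lipid and CPK values of the same type in two or more participants. They are asymptomatic values, unless CPK is read without the symptom limit. The documents give no rate for such values, so no frequency can be stated. The cases in the table compare readings of a sentence; they do not estimate how often a pause would be missed or triggered.

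A reader might infer that serious lipid or CPK toxicity could go unreviewed, or that the sponsor means to exempt the worse grade. The documents support neither. The separate bullet and the sponsor's ongoing review cover clinically significant Grade 4 events, and the misplaced exception looks like a drafting slip. No endpoint, estimand or analysis is affected.

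This rests on one assumption: in the Grade 4/SAE bullet, clinical significance and attribution are taken to qualify the Grade 4 event as well as the SAE.

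**What to change.** Move the exception after both arms and state symptom status and grade for each analyte, so that no higher grade is exempt while a lower grade pauses. For example: any Grade 3 or Grade 4 laboratory abnormality of one type "that the investigator considers reasonably attributable to VH4524184, in two or more participants", except asymptomatic Grade 3-4 lipid abnormalities and asymptomatic Grade 3-4 CPK increases.

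The downside is a looser rule than the literal text for asymptomatic Grade 3 lipids, and possibly for Grade 3 CPK. Exclusion criterion 25 hints at these grades but does not establish them for pausing, so the sponsor should confirm them. If the sponsor wants Grade 3 values of either analyte to pause, the coherent alternative is to delete the exception for that analyte, so that both grades pause.

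The cost is one protocol sentence, with no added visits, participants or analyses.

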8.4 Adverse Events (AEs) serious adverse events (SAEs), and other safety reporting

For definitions relating to safety information see Section 10.3

The investigator and any qualified designees are responsible for detecting, documenting, and recording events that meet the definition of an AE or SAE and remain responsible for following up AEs that are serious, considered related to the study intervention or study procedures, or that caused the participant to discontinue the study intervention or study (see Section 7). This includes events reported by the participant (or, when appropriate, by a caregiver, surrogate, or the participant's legally authorized representative).

The method of recording, evaluating, and assessing causality of AEs and SAEs and the procedures for completing and transmitting SAE reports are provided in Section 10.3 (AEs and SAEs: Definitions and procedures for recording, evaluating, follow-up, and reporting), and/or Section 10.6 (Division of AIDS Table for Grading the Severity of Adult and Pediatric Adverse Events).

8.4.1 Time period and frequency for collecting AEs and SAEs

All SAEs will be collected from the signing of the ICF until the final follow-up visit. Medical occurrences that begin before the start of study intervention but after obtaining informed consent will be recorded as medical history/current medical conditions, not as AEs.

All SAEs will be recorded and reported to the sponsor or designee immediately and under no circumstance should this exceed 24 hours, as indicated in Section 10.3 and/or Section 10.7. The investigator will submit any updated SAE data to the sponsor within 24 hours of it being available.

A post study AE/SAE is defined as any event that occurs outside of the AE/SAE reporting period defined in Section 10.3.6.

Investigators are not obligated to actively seek information on AEs or SAEs after conclusion of the study participation. However, if the investigator learns of any SAE, including a death, after a participant has been discharged from the study, the investigator must record it in the medical records. If the investigator considers the event to be reasonably related to the study intervention or study participation, the investigator must promptly notify the sponsor.

8.4.2 Method of detecting AEs and SAEs

Care will be taken not to introduce bias when detecting AEs and SAEs. Open-ended and nonleading verbal questioning of the participant is the preferred method to inquire about AE occurrences.

8.4.3 Follow-up of AEs and SAEs

After the initial AE/SAE report, the investigator is required to proactively follow each participant at subsequent visits/contacts. All SAEs will be followed until resolution, stabilization, the event is otherwise explained, or the participant is lost to follow-up (as defined in Section 7.3). Further information on follow-up procedures is provided in Section 10.3.6.5.

8.4.4 Regulatory reporting requirements for SAEs

- Prompt notification by the investigator to the sponsor of an SAE is essential so that legal obligations and ethical responsibilities toward the safety of participants and the

safety of a study intervention under clinical investigation are met. See Section [8.4.1](#) for reporting timeframes.

- For SAEs, the investigator must always provide an assessment of causality at the time of the initial report, as defined in the Section [10.3.6.3](#).
- An investigator who receives an investigator safety report describing an SAE or other specific safety information (e.g., summary or listing of SAEs) from the sponsor will review and then file it along with the IB and will notify the IRB/IEC, if appropriate according to local requirements.
- Investigator safety reports must be prepared for SUSARs according to local regulatory requirements and sponsor policy and forwarded to investigators as necessary.

8.4.5 Pregnancy reporting

Participants who become pregnant after the first study intervention dose must not receive subsequent doses of the study intervention but may continue other study procedures at the discretion of the investigator.

- Details of all pregnancies in female participants will be collected after the start of study treatment in the Monotherapy Period (Day 1) and until the final visit in the Follow-up Period (Day 38). Report all pregnancies to the Medical Monitor.
- If a pregnancy is reported, the investigator will record pregnancy information on the appropriate form (initial notification form or pregnancy follow-up form) and submit it to the sponsor within 24 hours of learning of the female participant's pregnancy (see Section [10.3.7](#)).
- Any pregnancy complication or elective termination of a pregnancy for medical reasons will be reported as an AE or SAE.
- Abnormal pregnancy outcomes (e.g., spontaneous abortion, fetal death, stillbirth, congenital anomalies, ectopic pregnancy) are considered SAEs and will be reported as such.
- The participant will be followed to determine the outcome of the pregnancy. The investigator will collect follow-up information on the participant and the neonate and the information will be forwarded to the sponsor. See Section [10.3.7](#) for reporting timeframes.
- Any poststudy pregnancy-related SAE considered reasonably related to the study intervention by the investigator will be reported to the sponsor as described in Section [8.4.4](#). While the investigator is not obligated to actively seek this information in former study participants, he or she may learn of an SAE through spontaneous reporting.
- All investigators are strongly encouraged to report all pregnancies exposed to standard of care ART to the Antiretroviral Pregnancy Registry (APR) as soon as the pregnancy is identified. Pregnancies can be reported to the Registry at [contact] via the data forms available at www.APRegistry.com.

8.4.6 Cardiovascular events and death events

For any CV events detailed in Appendix Section 10.3.4 and all deaths, whether or not they are considered SAEs, specific CV and Death sections of the eCRF will be required to be completed. These sections include questions regarding CV (including sudden cardiac death) and non-CV death.

The CV eCRFs are presented as queries in response to reporting of certain CV MedDRA terms. The CV information should be recorded in the specific CV section of the eCRF within 1 week of receipt of a CV Event data query prompting its completion.

The Death eCRF is provided immediately after the occurrence or outcome of death is reported. Initial and follow-up reports regarding death must be completed within 1 week of when the death is reported.

8.4.7 Disease-related events and/or disease-related outcomes not qualifying as AEs or SAEs

The events or outcomes listed in the CDC Classification System for HIV-1 Infections (Section 10.7) will be recorded on the HIV-Associated Conditions eCRF page if they occur. However, these individual events or outcomes, as well as any sign, symptom, diagnosis, illness, and/or clinical laboratory abnormality that can be linked to any of these events or outcomes are not reported to VH/GSK as AEs and SAEs even though such event or outcome may meet the definition of an AE or SAE, **unless the following conditions apply:**

- The investigator determines that the event or outcome qualifies as an SAE under part 'f' of the SAE definition (Section 10.3.2), or
- The event or outcome is in the investigator's opinion of greater intensity, frequency or duration than expected for the individual participant, or
- The investigator considers that there is a reasonable possibility that the event was related to study intervention.
- Death occurring for any reason during a study, including death due to a disease-related event, will always be reported promptly, or
- Lymphomas and invasive cervical carcinomas are excluded from this exemption; they must be reported as SAEs even if they are considered to be HIV-related.
- If any of the above conditions are met then record the DRE on the SAE page rather than the HIV Associated Conditions eCRF.

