- The disease/disorder being studied or expected progression, signs, or symptoms of the disease/disorder being studied, unless more severe than expected for the participant's condition.
- Medical or surgical procedure (e.g., endoscopy, appendectomy): the condition that leads to the procedure is the AE.
- Situations in which an untoward medical occurrence did not occur (social and/or convenience admission to a hospital, admission for routine examination.).
- Anticipated day-to-day fluctuations of pre-existing disease(s) or condition(s) present or detected at the start of the study that do not worsen. Pre-existing diseases will be recorded in the medical history section of the eCRF.
- Hospitalization for elective treatment of a pre-existing condition (known or diagnosed before signing the informed consent) that did not worsen from baseline.
- DRE, typically associated with the disease under study. These events will be recorded in the participant's eCRF and will be monitored by SRT on a routine basis. However, if 1 or both of the following conditions apply, then the event should be reported promptly to VH/GSK as an SAE (see Section 8.4.8):
 - The event is, in the investigator's opinion, of greater intensity, frequency, or duration than expected for the individual participant, or
 - The investigator considers that there is a reasonable possibility that the event was related to the administration of the study intervention

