10.3.2 Definition of SAE

An SAE is defined as any untoward medical occurrence that, at any dose, meets one or more of the criteria listed:

a. Results in death

b. Is life threatening

The term 'life-threatening' in the definition of 'serious' refers to an event in which the participant was at risk of death at the time of the event. It does not refer to an event, which hypothetically might have caused death, if it were more severe.

c. Requires inpatient hospitalization or prolongation of existing hospitalization

- In general, hospitalization signifies that the participant has been admitted (usually involving at least an overnight stay) at the hospital or emergency ward for observation and/or treatment that would not have been appropriate in the physician's office or outpatient setting. Complications that occur during hospitalization are AE. If a complication prolongs hospitalization or fulfills any

other serious criteria, the event is serious. When in doubt as to whether “hospitalization” occurred or was necessary, the AE should be considered serious.

 • Hospitalization for elective treatment of a pre-existing condition that did not worsen from baseline is not considered an AE.

 d. Results in persistent or significant disability/incapacity

 • The term disability means a substantial disruption of a person’s ability to conduct normal life functions. • This definition is not intended to include experiences of relatively minor medical significance such as uncomplicated headache, nausea, vomiting, diarrhea, influenza, and accidental trauma (e.g., sprained ankle) that may interfere with or prevent everyday life functions but do not constitute a substantial disruption.

 e. Is a congenital anomaly/birth defect in the offspring of a study participant

 f. Abnormal pregnancy outcomes (e.g., spontaneous abortion, fetal death, stillbirth, congenital anomalies, ectopic pregnancy)

 g. Is a suspected transmission of any infectious agent via an authorized medicinal product

 h. Other situations:

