
 • Possible Hy’s Law case: ALT \geq 3x ULN AND total bilirubin \geq 2x ULN ($>35\%$ direct bilirubin) or INR >1.5 must be reported as SAE • Medical or scientific judgment should be exercised by the investigator in deciding whether SAE reporting is appropriate in other situations such as significant medical events that may jeopardize the participant or may require medical or surgical intervention to prevent one of the other outcomes listed in the above definition. These events should usually be considered serious. 
 ○ Examples of such events include invasive or malignant cancers, intensive treatment for allergic bronchospasm, blood dyscrasias, convulsions, or development of intervention dependency or intervention abuse.

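### The first exception to the HIV-event reporting exemption in Section 8.4.7 cites SAE part f (pregnancy outcomes), so it reaches no CDC-listed condition, and Section 10.3.1 gives a shorter list of exceptions

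*Protocol*

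**What the plan says.** Protocol Section 8.4.7 directs the conditions in the CDC classification (Section 10.7), and any sign, symptom, diagnosis or laboratory abnormality linked to them, to the HIV-Associated Conditions eCRF page. These "are not reported to VH/GSK as AEs and SAEs even though such event or outcome may meet the definition of an AE or SAE", unless a listed condition applies, in which case the event moves to the SAE page. The first condition is "The investigator determines that the event or outcome qualifies as an SAE under part" f of the definition in Section 10.3.2; four others follow.

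In Section 10.3.2 the part with that letter is "f. Abnormal pregnancy outcomes (e.g., spontaneous abortion, fetal death, stillbirth, congenital anomalies, ectopic pregnancy"). The clause on medically significant events is two letters further down, under "h. Other situations". It says that "Medical or scientific judgment should be exercised by the investigator in deciding whether SAE reporting is appropriate in other situations", and the same part makes a possible Hy's law case an SAE.

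Section 10.3.1 states the exemption a second time, for disease-related events, among events that do not meet the AE definition. It says the Safety Review Team (SRT) will monitor such events routinely, then adds: "However, if 1 or both of the following conditions apply, then the event should be reported promptly to VH/GSK as an SAE". Only two conditions follow.

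**The concern.** This rule decides, event by event, whether a site files an SAE report or fills in a different page. If its first exception points to the wrong part of the SAE definition, one class of serious event loses a route back into SAE reporting. Such an event would not be sent to the sponsor within 24 hours (Section 8.4.1) and would not enter the AE and SAE summaries in SAP Section 4.3.2.1. SAP Section 6.1.2 makes HIV-associated conditions available only at participant level in the data viewer, and the SAP text plans no summary table for them.

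The second statement of the rule, in Section 10.3.1, adds a separate problem. Two sites that rely on different sections could handle the same event differently.

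**Working it through.** No arithmetic is needed for the cross-reference; the check sets the sections side by side.

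**Step 1: what the cited letter means.** The lettered parts of Section 10.3.2 are:

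| Part | Subject |
|---|---|
| a | death |
| b | life-threatening |
| c | hospitalization |
| d | disability |
| e | congenital anomaly |
| f | abnormal pregnancy outcomes |
| g | transmission of an infectious agent |
| h | other situations: possible Hy's law; medically significant events by investigator judgment |

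Section 8.4.7 cites f and does not cite h. None of the stage-3-defining illnesses in Section 10.7 is a pregnancy outcome, so the first exception applies to none of them. Section 8.4.5 already makes abnormal pregnancy outcomes SAEs, so the reference adds nothing as it stands. The text of all three sections is intact, so redaction does not explain the mismatch.

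**Step 2: which exceptions remain, and whether the two lists agree.**

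| Condition that lifts the exemption | 8.4.7 | 10.3.1 |
|---|---|---|
| SAE under the cited part | yes, but cites f | no |
| Worse than expected for the participant | yes | yes |
| Possibly related to study intervention | yes | yes |
| Death from any cause | yes | no |
| Lymphoma or invasive cervical carcinoma | yes | no |

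Section 10.3.1 has two of the five conditions. On a lymphoma judged unrelated and no worse than expected, 8.4.7 requires an SAE report, while 10.3.1 read alone treats it as not an AE.

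**Step 3: what falls through in 8.4.7.** Removing the events covered by the four working exceptions leaves a non-fatal event, not lymphoma or invasive cervical carcinoma, that the investigator considers unrelated and no worse than expected. Among these, the wrong letter matters for events that are serious under the medically significant clause. Newly diagnosed Kaposi's sarcoma is an example. It is on the Section 10.7 list, it is outside the lymphoma and cervical carve-out, and invasive or malignant cancers are among the examples given under part h. A reference to h could reach it; a reference to f cannot.

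Possible Hy's law shows a related conflict. Section 8.4.7 exempts laboratory abnormalities linked to a listed condition, while Sections 10.3.2, 10.3.7 and 10.5 require possible Hy's law cases to be reported as SAEs.

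**Step 4: the pausing rules (Section 8.3.7).** Death is its own criterion and is also an exception in 8.4.7. The arrhythmia criterion needs no attribution, but arrhythmia is not a CDC-listed condition. The remaining criteria require attribution to the drug, and an investigator who attributes the event has already lifted the exemption. One gap is left. The criterion for Grade 4 events and SAEs accepts attribution by the investigator or the sponsor, whereas the relatedness exception in 8.4.7 depends on the investigator alone.

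**Step 5: how much exposure is at stake.** Entry requires a CD4 count of at least 200 cells/mm³ (Section 5.1) and no active Stage 3 disease apart from cutaneous Kaposi's sarcoma not needing systemic therapy (Section 5.2.1). With about 28 participants followed to Day 38, total follow-up is about 28 × 38 = 1,064 participant-days, or 1,064 / 365.25 ≈ 2.9 participant-years. The documents give no event rate, so no expected count can be calculated.

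**The case against.** The strongest reply is that the exemption is deliberate and most of the consequence comes from it, not from one letter. Section 8.4.7 openly removes events that meet the SAE definition. A listed illness that is serious only because of hospitalization (part c) gets no exception of its own whether the letter is f or h. That is correct, and it limits the point to events serious under whichever part was meant.

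A participant with a CD4 count of at least 200 who develops a serious opportunistic illness within 38 days might well be judged worse than expected, which lifts the exemption. This is plausible, but it rests on investigator judgment and is not assured. HIV-associated conditions are also asked about at every scheduled visit or call, so the events are captured.

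On Section 10.3.1, one can say that it names two triggers for reporting without declaring them the only ones, so 8.4.7 merely adds to it. That softens the conflict. Even so, a site using 10.3.1 alone finds no instruction for lymphoma, invasive cervical carcinoma or death, although 8.4.7 makes reporting them mandatory.

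A reader might infer three stronger things that the documents do not support:

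- **That all medically important HIV-related events stay exempt.** Four other exceptions still operate.
- **That the pausing rules are disabled, or the events hidden from the sponsor.** Attribution by the investigator restores reporting, and Section 10.3.1 has the SRT review disease-related events routinely.
- **That the protocol shows h was meant.** It does not say. Read literally, f could still apply to a pregnancy outcome linked to a listed illness, although Section 8.4.5 already covers that case.

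**Conclusion.** The point holds as an internal inconsistency in an operative safety-reporting rule: wrong as written, and minor in size. The mismatch between the cited letter and the lettered list is certain. The affected class is the narrow one isolated in step 3. For that class the loss is the 24-hour report and the place in the AE/SAE tables. The pausing-rule effect is confined to events that only the sponsor would attribute to the drug. The mismatch between 8.4.7 and 10.3.1 stands whatever part was intended.

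Two assumptions carry the conclusion: that sites apply the text literally, and that a medically significant event was the intended target. The second is a likely inference and needs the sponsor's confirmation. The number of affected events should be very small, possibly zero, and no antiviral endpoint depends on it.

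**What to change.** The sponsor should state which part of the SAE definition the first bullet of Section 8.4.7 was meant to cite, and cite it there by name as well as letter so that later relettering cannot break it. It appears to be h, Other situations. The condition list in Section 10.3.1 should then be made identical to the one in 8.4.7, or replaced by a cross-reference to it.

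The cost is one corrected reference and one aligned list in the protocol text. No analysis, sample size or visit schedule changes.
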